Assessments of Safety	
Safety evaluations will include adverse event (AE) and serious AE (SAE) reporting, electrocardiograms, vital signs (temperature, respiratory rate, blood pressure, and heart rate), physical examination, body weight and height, laboratory parameters (hematology, biochemistry, and urinalysis), urine pregnancy tests for FOCBP, and concomitant medication reporting. Concomitant medications will include treatment per standard of care, which may or may not include corticosteroids (eg, prednisone at 2 mg/kg PO to a maximum dose of 100 mg daily) for 4 days.
 
Evaluation of subjects under the age of 18 enrolled with open epiphyses will include knee (anterior/posterior [AP] view) and hand-wrist radiographs (posterior/anterior [PA] view) for assessment of epiphyseal growth plate and distal femoral angle; tibial and femoral long bone lengths; and standardized stadiometry and knee height for assessments of linear growth (in triplicate). If there is evidence of partial or complete premature growth plate closure (with or without growth deceleration) study drug may be continued, interrupted, de-escalated, or discontinued. Dose modification decisions will be made by the Investigator upon review of the subject's clinical and radiographic information, and following discussion of the risk/benefit with the subject/parent. The Investigator may consult with the sponsor and the DMC.
 
In addition, bilateral hand-wrist and knee growth plate morphology will be assessed by WBCT scan safety read (performed every 6 months up to Month 24 in Part A, and annually thereafter in Parts B and C). Bilateral hip growth plate morphology will also be assessed for avascular necrosis in all subjects. Limb/joint AEs in these subjects will be evaluated by clinical and radiographic assessments as deemed appropriate by the Investigator.
 
Adverse event severity will be assessed and reported according to criteria defined in the protocol (mild, moderate, severe).
 
Adverse events known to be associated with retinoids (eg, mucocutaneous events) will be further graded according to the Common Terminology Criteria for Adverse Events (CTCAE), Version 4.03, 14 June 2010.

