### **7.2.3 Body Weight and Linear Growth Assessments**

All subjects will have body weight assessed at Screening and every 3 months in Part A (Months 3, 6, 9, 12, 15, 18, 21, and 24) and Part B (Months 27, 30, 33, 36, 39, 42, 45, and 48), Part A or B EOT/EOS and Part C (Years 1 and 2 or SC post last dose of study treatment).

For subjects receiving flare-up-based treatment in Parts A and B, body weight will also be recorded at Flare-up Cycle Safety Day 1 and every 12 weeks thereafter during safety assessments until treatment of the last flare-up or traumatic event in the flare-up cycle is completed.

Subjects 18 years of age and older will have linear growth assessed by stadiometer at Screening in Part A. Subjects under the age of 18 years enrolled with open epiphyseal growth plates will

have linear growth assessments (in triplicate) by stadiometer and knee height measurements (in triplicate) at Screening and every 6 months (Months 6, 12, 18, and 24). Once a subject is 18 years old, triplicate linear growth and knee height assessments will no longer be required. The 6-month assessments of linear growth in subjects under the age of 18 years will continue in Part B (Months 30, 36, 42, and 48), Part A or B EOT/EOS and Part C (Years 1 and 2 or SC post last dose of study treatment)

Linear growth measurements will be performed by trained and qualified study personnel at the same time of day for each assessment, if possible. The stadiometric measurement instructions will include practices that reduce measurement error including calibration of equipment, proper subject positioning, and measurement capture. The same examiner should be used whenever possible to standardize the performance of procedures and minimize the inter-examiner variability. Measurement of knee height will also be standardized.

In addition, the length of bilateral tibia and femur will be assessed by WBCT scan every 6 months up to Month 24 in Part A; and annually up to Month 48 in Part B; and annually in the NHS.

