2.1.3 Efficacy Endpoints

Primary Efficacy Endpoint

The primary efficacy endpoint is the annualized change in new HO volume as assessed by low-dose, WBCT, excluding head. The annualized change in new HO volume will be compared between treated and untreated subjects. WBCT scans are performed at baseline, Month 12,

Month 24 and Month 36 in the NHS and at baseline, Month 6, Month 12, Month 18 and Month 24 in the MOVE Trial. WBCT scans may also be performed at the time of early study discontinuation.

As described in the MOVE Trial and NHS Independent Review Charter, HO volume is assessed by two independent readers blinded to study and timepoint, with adjudication by a third independent reader. HO volume is measured by body region with the baseline scan. The following 9 anatomical regions will be used to describe HO location:

- Right chest, neck, shoulder through mid-humerus
- Left chest, neck, shoulder through mid-humerus
- Mid Torso: torso below shoulder regions and above iliac crests
- Right arm: mid-humerus through hand
- Left arm: mid-humerus through hand
- Right hip: iliac crest, hip through mid-femur
- Left hip: iliac crest, hip through mid-femur
- Right lower leg: mid-femur through foot
- Left lower leg: mid-femur through foot

In post-baseline scans, the presence of new HO within each body region and, if present, the HO volume within the body region, are measured. The primary efficacy analysis described in [Section 0](#) models the number of body regions with new HO compared to the previous scan and the volume of new HO within each body region with new HO compared to the previous scan as the unit of measurement.

Note that the primary endpoint includes annualized HO based on the new HO observed up to Month 24 in MOVE and up to Month 36 in NHS. The sponsor believes that the new HO observed between Month 24 and Month 36 in NHS is relevant and that annualization is sufficient to protect against bias. Sensitivity analyses to assess impact of differences in length of follow-up between NHS and MOVE are described in [Section 2.4.4](#).

The primary efficacy endpoint, as well as the secondary endpoints that depend on the efficacy imaging, will not be summarized in the descriptive analysis to be conducted before the first formal interim efficacy analysis, due to the ongoing nature of the blinded reads.

Secondary Efficacy Endpoints

The following secondary efficacy endpoints will be assessed:

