- any difference in the assessment of presence of femoral head abnormalities (i.e., no vs. not evaluable vs. yes)
- any difference in the presence of hand/wrist and/or knee epiphyseal abnormalities (i.e., no vs. not evaluable vs. yes)

- any difference in the assessment of any epiphyseal abnormality change from TP1 and/or from prior timepoint in either the knee and/or hand/wrist (i.e., not present vs. no change vs. improved vs. worse vs. unknown)
- any difference in selected abnormality(ies) per location.

Given the granularity of the discrepancy evaluation, discrepancies of 30% or more are expected to occur for each review type.

Inter-Reader Agreement

To determine inter-reader agreement, the radiologists participating in primary radiology reviews will read a subset of eight study subjects for WBCT efficacy, eight study subjects for WBCT safety and four study subjects for radiograph read types, with a minimum of two timepoints each, randomly selected by Parexel's image management and review system at least 3 weeks after the initial radiology review. Discrepancies identified within the completed secondary review cases will be reviewed by Parexel as described below. Discrepancies are defined in IRC Section 14.1.1 (Intra-Reader Agreement).

If a secondary review results in discrepancies for more than 30% of the timepoints for a reviewer for each review type, Parexel medical personnel will review the discrepancies to assess whether preventative actions as described in IRC Section 14.2 (Quality Monitoring) are required.

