Note that bone safety analysis will also be performed based on premature physal closure status.

Analyses of Knee and Hand/Wrist Radiographs and WBCTs for Assessment of Bilateral Hand/Wrist and Knee Epiphyseal Growth Plate

The summary statistics of bone age and the difference between bone age and chronological age (ratio of change from baseline in bone age to change from baseline in chronological age) will be calculated for each visit.

Figures will include a by-subject spaghetti plot of the bone age by chronological age, and a summary figure by sex and age group (4-10, 11-18) with femur length and tibia length on the y-axis and visit on the x-axis. Similar figures will be produced using chronological age in place of bone age.

Summary tables of growth plate abnormalities identified in radiographs (MOVE Trial only) will include the following:

- Number and proportion of subjects with any abnormality at baseline, and by specific abnormality (e.g., growth recovery lines, sclerosis, etc.)
- Number and proportion of subjects with any new post-baseline or prior time point abnormality, and by specific abnormality
- Number and proportion of subjects with any new post-baseline or prior time point worsening, and by specific abnormality
- Number and proportion of subjects with improvement from baseline or prior time point abnormality, and by specific abnormality

Summary tables of growth plate abnormalities identified in WBCT safety reads (MOVE Trial and NHS) will include the following:

- Number and proportion of subjects with any abnormality at baseline, and by specific abnormality (e.g., growth recovery lines, sclerosis, etc.)
- Number and proportion of subjects with any new post-baseline or prior time point abnormality, and by specific abnormality
- Number and proportion of subjects with any new post-baseline or prior time point worsening, and by specific abnormality
- Number and proportion of subjects with improvement in baseline or prior time point abnormality, and by specific abnormality

Listings of all subjects with premature growth plate closure will be provided.

Bone Age

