Analyses of WBCT Measurements of Femur and Tibia Lengths The summary statistics of femur and tibia lengths (values and changes from baseline) will be calculated for each visit. Femur and tibia lengths will be summarized for the following subgroups:

- Male, Age 4-10 years
- Male, Age 11-18 years
- Female, Age 4-10 years
- Female, Age 11-18 years
- Female Age ≤ 8 , Male Age ≤ 10 years
- Female Age >8 to <14, Male Age >10 to <14 years
- Age ≥ 14 years

Figures will include spaghetti plots of the femur and tibia change from baseline by chronological age.

Leg Length Discrepancies

Leg length discrepancies will be calculated by the difference in right and left femur and tibia lengths as measured by low-dose WBCT. Potential clinically meaningful leg length differences

(ie, >1.5 cm difference) were compared with untreated NHS subjects by age category and PPC status.

Analyses of Evaluation of Bilateral Hips by WBCT Safety Read

Summary tables of hip abnormalities identified in WBCT safety reads (MOVE Trial and NHS) will include the following:

- Number and proportion of subjects with possible, probable, or definite avascular necrosis (AVN) at baseline, and by specific abnormality (e.g., subchondral lucency, osteosclerosis, etc.)
- Number and proportion of subjects with any new post-baseline or prior time point AVN, and by specific abnormality
- Number and proportion of subjects with any new post-baseline or prior time point worsening in AVN, and by specific abnormality
- Number and proportion of subjects with improvement in baseline or prior time point AVN, and by specific abnormality

Assessments for Spinal Health

WBCT scan assessments described above, will also be used to analyze spinal bone mineral density, bone strength, bone mineral content and fractures, utilizing biomechanical computed tomography (BCT) analysis. These results will be compared to NHS subjects (Study PVO-1A-001). To assess potential effect of palovarotene on these parameters modeling will be performed at month 12 with comparison to NHS subjects. Additionally descriptive statistics will be provided for each timepoint.

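### The CT growth-plate and hip tables compare MOVE with NHS on any-new-finding counts without fixing the number of reads or the follow-up, so the proportions are not comparable

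*SAP*

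**What the plan says.** SAP 2.4.5 plans two sets of CT safety-read tables that cover both studies. For hand/wrist and knee growth plates, one row is "Number and proportion of subjects with any new post-baseline or prior time point abnormality, and by specific abnormality". For the hips, the matching row is "Number and proportion of subjects with any new post-baseline or prior time point AVN, and by specific abnormality". Each set also has rows for worsening and for improvement, again against baseline or the prior scan. No row names a visit, a time window, an exposure adjustment or a maximum number of reads.

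The schedules differ. SAP 2.1.3 gives NHS a baseline and a one-year scan, and lists the remaining scans as "Month 24 and Month 36 in the NHS and at baseline, Month 6, Month 12, Month 18 and Month 24 in the MOVE Trial". The Protocol Synopsis says the MOVE CT safety read is "performed every 6 months up to Month 24 in Part A, and annually thereafter in Parts B and C". Protocol 7.2.3, on long-bone length by CT, gives the schedule as "every 6 months up to Month 24 in Part A; and annually up to Month 48 in Part B; and annually in the NHS".

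Follow-up limits are stated only for the efficacy endpoint, which uses "the new HO observed up to Month 24 in MOVE and up to Month 36 in NHS". For bone safety, SAP 2.4.5 (Bone Safety Assessments) splits MOVE into an original baseline period ending February 2020, an interruption period and a new baseline period. It gives no matching NHS window.

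**The concern.** A subject enters these rows if any one read shows something new or worse. That proportion grows with the number of reads whenever a finding can come and go or be misread, and it grows with follow-up for any finding. Within 24 months MOVE has four post-baseline reads and NHS has two. The prior scan is 6 months back in MOVE and 12 months back in NHS, so rows based on it do not measure the same thing in the two columns.

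The SAP accepts this mechanism for efficacy. The sensitivity analyses in 2.4.4 collapse MOVE to annual scans because identical bone growth counts twice in MOVE and once in NHS. Nothing equivalent is planned for the harm tables. Among the bone CT outcomes, only spinal health has a stated common time point with NHS (Month 12).

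What is at stake is the reading of a key harm. The radiograph abnormality tables are MOVE only, so the CT tables are the only planned growth-plate abnormality tables with an untreated column.

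**Working it through.** **Inputs from the documents.** Post-baseline reads to Month 24: MOVE 4, NHS 2. NHS to Month 36: 3 (SAP 2.1.3). If Parts B and C are pooled, MOVE has up to 6 reads, at Months 6, 12, 18, 24, 36 and 48 (Protocol Synopsis).

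**Assumed inputs.** The documents give no per-read probability q of a transient or misread finding, no yearly rate h of persistent findings and no duration of findings. Ranges are shown. Every step assumes no drug effect.

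**Step 1: the SAP's own illustration (2.4.4).** Growth of 8000 mm³ split over two 6-month intervals gives 2 events in MOVE and 1 in NHS. The per-event ratio is 8000/4000 = 2, or √8000/√4000 = 1.41 after square-root transformation. Both figures reproduce.

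**Step 2: transient or misread findings.** With independent reads, P(any) = 1 − (1 − q)^k for k reads. At q = 5%: 1 − 0.95⁴ = 0.185, 1 − 0.95² = 0.098 and 1 − 0.95³ = 0.143.

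| q | MOVE, 4 reads | NHS, 2 reads (Month 24) | Ratio | NHS, 3 reads (Month 36) | Ratio |
|---|---|---|---|---|---|
| 2% | 7.8% | 4.0% | 1.96 | 5.9% | 1.32 |
| 5% | 18.5% | 9.8% | 1.90 | 14.3% | 1.30 |
| 10% | 34.4% | 19.0% | 1.81 | 27.1% | 1.27 |

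**Step 3: persistent findings, read without error.** P = 1 − exp(−hT), with T in years. At h = 0.10, both studies show 18.1% at 24 months, a ratio of 1.00. With MOVE at 24 months and NHS at 36 it is 18.1% against 25.9%, a ratio of 0.70. For h from 0.02 to 0.20 that second ratio runs from 0.67 to 0.73.

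**Step 4: findings that last a while.** This is a simulation with onset rate 0.1 per year and exponential duration. For mean durations of 3, 6, 12 and 24 months the MOVE/NHS ratio is 1.74, 1.47, 1.23 and 1.12 at equal 24 months. Against NHS to Month 36 it is 1.17, 0.99, 0.84 and 0.77.

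**Step 5: both kinds together, NHS to Month 36.** MOVE is 1 − exp(−2h)(1 − q)⁴ and NHS is 1 − exp(−3h)(1 − q)³. MOVE is higher only if q > 1 − exp(−h), which is 2.0%, 4.9%, 9.5% and 18.1% for h = 0.02, 0.05, 0.10 and 0.20.

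**Step 6: pooling Parts A to C.** With six reads against three, step 2 gives 26.5% against 14.3% at q = 5%.

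**Step 7: common visits.** With Months 12 and 24 only in both studies, k = 2 and T = 24 months in each column, so the ratio is 1.00 for every q and h above.

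**The case against.** A reader might infer that MOVE must show more harm than NHS even if the drug does nothing. The documents do not support that. The excess needs findings that are transient or misread, and equal follow-up. Established, reliably read findings show none, and an NHS column running to Month 36 can cancel or reverse it.

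Other points have force.

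- The tables are descriptive, with no test planned. At equal follow-up the bias runs against the drug, which for harms is the cautious direction.
- The serious identified risk is premature physeal closure. SAP 2.1.4 lists closure as a radiograph parameter, and premature closures are listed subject by subject. Established closure would also be persistent.
- Protocol 3.3 reports dense metaphyseal lines in about 70% of subjects at both baseline and later. That limits how many subjects can have a first new finding of that type.
- Independence of reads is a simplification. Scans are compared with earlier scans, two radiologists read them, and hip disagreements are adjudicated. This lowers q and the effective number of independent reads without making the schedules equal.
- The bone-safety periods make pooling of six reads less likely, although Protocol 8.5.3 does plan an overall summary of Parts A, B and C.

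Two further inferences should be resisted. The SAP 2.1.5 remark that "discrepancies of 30% or more are expected to occur for each review type" describes disagreement on re-reading under a fine-grained definition. It is not a false-positive rate and does not set q. The leg-length comparison with NHS is a measured difference, and no bias from read frequency has been shown for it.

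These points limit the size and direction of the bias. They do not make the columns comparable.

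**Conclusion.** The point holds as a comparability problem of unsettled direction. As written, the between-study rows mix any drug effect with read frequency and with follow-up that the SAP does not fix. At equal 24 months, transient or misread findings inflate MOVE by a factor of about 1.8 to 2 under independent reads with q of 2% to 10%, and by less for longer-lasting findings. Persistent, reliably read findings give a ratio of 1.00. With NHS counted to Month 36, the factor falls to about 1.3 for misread findings and to about 0.7 for persistent ones, so the table could overstate a harm or hide one. All sizes rest on assumed values of q, h and duration. The unequal schedules and the missing window come straight from the documents.

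**What to change.** In the growth-plate and hip CT parts of SAP 2.4.5:

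- Make the MOVE-against-NHS rows a common-visit table using baseline, Month 12 and Month 24 in both studies, with NHS capped at Month 24.
- Define new, worse and improved against baseline only. The reads already carry this: SAP 2.1.4 for hips, and the change-from-first-timepoint item in SAP 2.1.5 for growth plates.
- Restrict MOVE scans to the original baseline period (through February 2020), so that Month 24 does not mix on-drug scans with those from the long interruption. Because dosing stopped on 4 December 2019 for subjects under 14 and about 24 January 2020 for the rest, this limits off-drug scans but does not remove them all.
- Show the number of subjects read at each visit. SAP 1.4 expected the 18-month analysis in mid-May 2020, so later enrollees will not have reached Month 24 within that period.
- Put the Month 6, Month 18, later-period and Part B/C reads, and every row based on the prior scan, in MOVE-only tables.
- Footnote that MOVE Month 12 and 24 scans may have been read with Months 6 and 18 available, a limit that SAP 2.4.4 already states for the efficacy reads.

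The cost is SAP wording and a re-tabulation of existing reads. Month 6 and 18 findings leave the between-study table but stay visible for MOVE. Tables already run for the interim study report would have to be redone, although SAP 3.3 does not plan to rerun them.

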Subjects under the age of 18 years enrolled with open epiphyseal growth plates will have linear growth assessments (in triplicate) by stadiometer at Screening and every 6 months (Months 6, 12, 18, and 24). Measurement of knee height using a standard caliper will also be performed (in triplicate) at Screening and every 6 months (Months 6, 12, 18, and 24). Once a subject is 18 years old, triplicate linear growth and knee height measurement will no longer be required.

WBCT Measurements of Femur and Tibia Lengths

Although the WBCT scans obtained in the NHS and MOVE Trial are used primarily to quantify change in HO volume, they will also be used to assess the length of the femur and tibia bilaterally on all subjects aged 17 years and below.

Evaluation of Bilateral Hips by WBCT Safety Read

Although the WBCT scans obtained in the NHS and MOVE Trial are used primarily to quantify change in HO volume, they will also be used to assess potential adverse effects on the femoral head related to avascular necrosis of the hip (AVN).

Two independent radiology reviewers will qualitatively assess the hip joints on WBCT scan to determine whether there is evidence of AVN. Discrepancies in the reads will be adjudicated. Each hip will be assessed for presence or absence of AVN and, if present, the degree of change from the baseline scan and previous scan.

Trauma Leading to Flare-up

In MOVE, subjects can initiate flare-up dosing for substantial high-risk traumatic events likely to lead to a flare up. A listing of traumatic events and whether the trauma resulted in a confirmed flare-up will be generated.

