Bone age is assessed by hand/wrist radiographs. To normalize change in bone age over time, the ratio of change from baseline in bone age to change from baseline in chronological age will be calculated such that a ratio of 1 indicates the same progression over time, while a ratio >1 indicates faster progression of bone age relative to chronological age. Descriptive statistics will be analyzed by timepoint.

Bone age will also be assessed by age category and premature physal closure (PPC) status.

Analyses of Knee Alignment

Summary statistics of lateral distal femoral angles will be calculated for each visit and new-onset potentially clinically significant knee lateral distal femoral angles (i.e. angles outside of the physiological range defined as 78.9 to 84.9 degrees). Listings will also be generated for subjects meeting PCS criteria overall and by PPC status.

Analyses of Standardized Stadiometry and Knee Height for Assessments of Linear Growth

The summary statistics of linear height for age z-score and knee height (values and changes from baseline) will be calculated for each visit. Figures will include height z-scores over time and knee height over time. In addition, summary statistics of weight for age z-score and BMI (kg/m^2) for age z-score (values and changes from baseline) will be calculated for each visit and plotted against age.

The z-scores will be calculated by using US Centers for Disease Control and Prevention (CDC) growth charts, using the SAS macro from <http://www.who.int/childgrowth/software/en/>. (Note that the derivation of the z-scores depends on sex and age in months.)

Growth velocity will also be summarized in tables and figures. The calculation of growth velocity will be performed as follows: $((\text{Current Height} - \text{Previous Height}) / (\text{duration (days)} = (\text{current date} - \text{previous date}))) * 365.25 = \text{Annualized Growth Velocity (cm/year)}$. In addition to providing the calculated growth velocities per time period for each subject, the data will also be categorized according to worst growth velocity and last growth velocity by the following three categories: <4 cm/year; 4 to 5 cm/year; and >5 cm/year.

Growth assessments (linear height, knee height, and femur and tibia lengths and growth velocity over 12 months) will also be assessed by age category, treatment status and premature physeal closure (PPC) status.

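### Femur and tibia growth in MOVE and NHS is tabulated as raw change in wide age bands with no age adjustment, so the comparison is open to confounding by age and to dilution by children who have stopped growing

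*SAP*

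**What the plan says.** SAP 2.4.5 gives one rule for CT long-bone length: "The summary statistics of femur and tibia lengths (values and changes from baseline) will be calculated for each visit". It lists seven subgroups. Four are sex-specific (4-10 and 11-18 years), for example "Male, Age 11-18 years". Three pool the sexes: girls up to 8 with boys up to 10; "Female Age >8 to <14, Male Age >10 to <14 years"; and everyone aged 14 or more.

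SAP 2.1.4 sets who is measured: the scans "they will also be used to assess the length of the femur and tibia bilaterally on all subjects aged 17 years and below". There is no open-plate condition.

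SAP 2.4.5 also plans a breakdown of the growth measures by age category, treatment status and premature physeal closure (PPC) status, and individual plots of femur and tibia change against chronological age. Its general rules add NHS data to WBCT summaries where applicable. Protocol 7.2.3 has these lengths read annually in NHS.

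Other measures are handled differently:
- **Stature and knee height (SAP 2.4.5):** "The summary statistics of linear height for age z-score and knee height (values and changes from baseline) will be calculated for each visit". Only height is standardised for age and sex.
- **Spine (SAP 2.4.5):** a model against NHS at month 12.
- **Efficacy (SAP 2.4.4):** sex and age at scan are in the primary model, and age and sex enter the covariate and propensity-score sensitivity analyses.

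**The concern.** Protocol 3.2 calls PPC a serious identified risk. Lost long-bone growth is its direct consequence, and CT length is a growth measure collected in both studies. Growth depends strongly on age and sex, and the groups are not randomised. A raw mean change over a band of several years reflects the age mix of that band as well as any drug effect.

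Two distortions follow. If MOVE children in a band are older than NHS children, they grow less without any drug effect, which looks like harm; if they are younger, harm is hidden. Separately, children in either group who have finished growing contribute near-zero change and shrink a true deficit. A reader of the tables could not tell these apart from a drug effect. The SAP adjusts the same non-randomised contrast for age and sex when assessing benefit, but not here.

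**Working it through.** The documents give no sample size, effect size or growth rate for this comparison, so there is no planned figure to reproduce.

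**Band width.** The label 11-18 covers eight integer ages. Lengths are read only to age 17, so seven apply in practice. The 4-10 band also covers seven. The pooled middle band spans six years for girls (8 to 14) and four for boys (10 to 14). The SAP does not say whether age is taken at baseline or at the visit.

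**Reason to expect an age difference (SAP 1.7).** About 45 of 90 NHS subjects (50%) are assumed to cross over, supplying 45 of the 80 MOVE subjects in the sizing (56%). If they enter after the assumed 1.5 to 2 years of NHS follow-up, the average over MOVE is 0.5625 × 1.5 = 0.8 to 0.5625 × 2 = 1.1 years. This is before any offset from newly recruited subjects, whose ages are not given.

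**Age gap, simple form (all inputs assumed).** Let annual growth be g(a) = g0(16 − a)/5 from age 11 to 16 and zero afterwards, with ages uniform on 11-18.
- Band mean = (1/7)(g0/5)(25/2) = 0.357 g0.
- Tilt the age density to 1/7 + k(a − 14.5). Mean age moves by k × 7³/12 = 28.58k, so a 1-year gap needs k = 0.0350.
- Mean growth changes by k(g0/5) × ∫(a − 14.5)(16 − a)da over 11 to 16 = 0.0350 × (g0/5) × (−22.92) = −0.160 g0.
- That is 0.160/0.357 = 45% of band growth, or 0.16 to 0.32 cm/year for g0 = 1.0 to 2.0. A 0.5-year gap gives half, about 22%.

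**Age gap, simulation (all inputs assumed).** Femur plus tibia growth falls linearly from 2 or 3 cm/year at age 11 to zero at 15 or 17. NHS ages are normal (mean 13.5, SD 2) truncated to 11 to <18. The MOVE mean is shifted up by 0.5, 1 or 2 years before truncation, with no drug effect.

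| Realised gap in band (years) | False MOVE deficit (cm/year) | Share of NHS growth |
|---|---|---|
| 0.3 | 0.11-0.17 | 10-17% |
| 0.7 | 0.21-0.33 | 20-32% |
| 1.3 | 0.41-0.63 | 40-58% |

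Truncation matters: a nominal 1-year shift is realised as about 0.7 years inside the band.

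**Dilution.** If a share c of both groups has stopped growing, a true deficit d appears as (1 − c)d: 90%, 75% or 50% of its size for c = 10%, 25% or 50%. With uniform ages on 11 to <18, c would be 1/7 = 14%, 2/7 = 29% or 3/7 = 43% for growth ending at 17, 16 or 15. In the band aged 14 and over (14 to 17 in practice) it would be 1/4 = 25%, 2/4 = 50% or 3/4 = 75%.

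**The case against.** The other side has real points. These are descriptive safety tables, and no test of femur or tibia length is planned. The harm itself is reported directly: premature closures are listed, growth-plate abnormalities on WBCT are tabulated for both studies, and height has a z-score and annualised velocity. Narrower bands, PPC-status breakdowns and plots by age are planned, and they cover the youngest children, for whom the protocol expects the growth impact to be greatest. Age mix by study is not documented, newly recruited subjects could offset the crossovers, and every input to the magnitudes above is assumed.

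Most of this stands as a limit on the point, but it does not remove it. The narrower bands pool the sexes, PPC status is itself a post-treatment outcome, and individual plots show but do not adjust. Closure listings count events; they do not measure lost growth.

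Stronger readings are tempting, and the documents do not support them:
- **That knee height shares the defect.** It is reported raw, but the seven subgroups are listed for femur and tibia only. Its follow-up is tied to immaturity at entry (Protocol 7.2.3 and Table 1), as is stadiometry: "Subjects under the age of 18 years enrolled with open epiphyseal growth plates will have linear growth assessments (in triplicate) by stadiometer". Children closed at baseline are therefore not in its follow-up; those who close on study are part of the outcome.
- **That the comparison is confounded.** The documents give a reason to expect an age difference, not evidence of one.
- **That the tables must understate harm.** An older MOVE group would exaggerate it while dilution hides it, so the net direction is unknown.

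**Conclusion.** The point holds for femur and tibia. As planned, a raw MOVE-NHS difference in these lengths cannot be separated from a difference in age mix, and a true deficit may be diluted by children who are no longer growing. The size cannot be derived from the documents. The illustrations show only that an age gap of well under a year could produce a false difference of a tenth to a third of NHS growth. They rest on assumed growth rates, ages at closure and age distributions. Knee height needs the same age and sex adjustment because it is raw, but for no further reason. This is an inexpensive improvement to a descriptive safety comparison; it does not show that the planned tables are wrong.

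**What to change.** In SAP 2.4.5, add a supportive mixed model for annualised femur growth and another for tibia growth, using the annual scans both studies share. Include treatment, baseline length, age as a continuous or spline term by sex, time, a treatment-by-age term so that the effect is reported at growing ages, and a subject random effect for those who contribute to both studies. State whether the bands use age at baseline or at the visit. Keep the raw tables. Apply the same age and sex adjustment to knee height where NHS has it.

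Restrict to plates open at baseline only as a sensitivity analysis, and only if an open/closed status already exists for both studies. SAP 2.1.4 lists only growth-plate abnormalities for the WBCT safety images, and the radiograph growth-plate summaries in SAP 2.4.5 are for MOVE only. Without an existing status, this would need a new central read. The restriction should use baseline status, because restricting at each interval would remove children whose plates closed on treatment.

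The cost is SAP wording, one extra model per measure on lengths the protocol already collects, and a modelling assumption for the age curve. It is also an added run, since SAP 3.3 does not plan to rerun interim-CSR analyses for the final report.
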